3.2.16 Covariates and analysis of subgroups

Subgroup analyses will be conducted by presenting the primary analysis of ORR (with point estimates and 95% CIs) for both independent central review (Tables 14.2.1.10 based on Efficacy population and 14.2.1.11 based on Per Protocol population) and Investigator's assessment (Tables 14.2.4.13 and 14.2.4.14) in the following subgroups:

- Age (<65 years, \geq 65 years);
- Gender (female, male);
- Memorial Sloan Kettering Cancer Center (MSKCC) Risk Factors (favourable [0], intermediate [1], poor [2 or more]);
- Heng criteria (favourable [0], intermediate [1-2], poor [3-6]);
- Number of organs with metastases (1, 2, \geq 3);
- ECOG (0, 1);
- Treatment duration on 1st anti-cancer therapy (<6 months, \geq 6 months).

Subgroup analyses will be presented in each cohort separately. In addition, ORR according to local Investigator's review per RECIST 1.1 will be presented in the overall population (cohort A + cohort B).

The age will be calculated as defined in [Appendix 1 \(22\)](#), and the treatment duration in [Appendix 1 \(18\)](#).

4 COMPUTER SYSTEMS, SOFTWARE AND VALIDATION OF PROGRAMS

4.1 Hardware

The statistical analysis will be performed using UNIX operating system.

4.2 Software

All tables, listings and figures will be produced, and statistical analysis performed using SAS® version 9.4 or a later version in a secure and validated environment. All outputs will be produced in Microsoft Word Format (RTF format) and will be combined into a PDF file(s).

4.3 Validation programs

All tables, figures and data listings to be included in the report will be independently checked for consistency, integrity and in accordance with standard Parexel procedures.

Program validation (including any macros) will be in accordance with Parexel's SOPs referenced in Project Specific SOP list.

Copies of the internal QC forms produced for the validation process and the Clinical Research Organisation (CRO)'s sign-off forms will be provided to the sponsor to support the validation.

SAP Final: Version 6.0: 17 August 2023

4.4 Restitution of the programs

All programs developed for this study for producing the analysis datasets, tables, listings and statistical output along with associated logs should be given to the sponsor when the tables, listings, figures and statistical analysis has been finalised.

5 CHANGES FROM PROTOCOL

The end of the recruitment being driven by the approval of the protocol amendment by competent authorities and/or ethics committees in each country, the sample size in cohort A exceeds the target of 74 subjects (see Section 1.2).

The included Population definition is revised to include the subjects who did not fulfil the inclusion and exclusion criteria (e.g. if non-compliance to inclusion or exclusion criteria is identified after inclusion in the study), but nevertheless received at least one dose of study medication (see Section 2).

Efficacy and Per Protocol populations are split for IRC assessments and investigator assessments (see Section 2.1).

Change from baseline in tumour size summaries (Tables 14.2.1.7, 14.2.1.8, 14.2.4.11 and 14.2.4.12) and corresponding waterfall plots (Figure 14.2.1.9 and Figure 14.2.4.12) are added for exploratory purpose (see Section 3.2.1.2).

The Adverse Events of Special Interest are added for exploratory purpose (see Section 3.2.2.1).

7 APPENDICES

Appendix 1: Derived Data

The following derived data will be calculated and included in the listings:

(1) Tumour assessments and best overall response (BOR)

In case of missing tumour assessment at visit n, it should be kept missing as long as the next evaluation at visit n+1 is a Progressive Disease (PD). The best overall response (BOR) in this case is 'not evaluable' if there are no previous assessments. Otherwise, the best overall response will be assessed by using tumour assessments up to visit n-1.

On the other hand, if the assessment at visit n+1 does not show any progression, this missing assessment (at visit n) will be derived by using the assessment from previous visit n-1 (last observation carried forward method). In this case the BOR will be assessed as defined.

(2) Time-to-response (TTR)

TTR is defined as the time from start of study treatment to the date of first evidence of response (PR or CR). For subjects with no evidence of response, the TTR will be censored at the last tumour assessment and considering the censoring rules defined in the table below.

| Event | Decision | Date of event or censoring |
|--|--------------|---|
| Response to treatment (PR or CR) with no more than one missing scheduled tumor assessment before the event and without NPACT before the event. | Not censored | Earliest date between: - date of PR - date of CR |
| Response to treatment (PR or CR) with two or more missing scheduled tumor assessments before the event | Censored | Date of the last tumor assessment prior to the missing assessment. |
| Response to treatment (PR or CR) with NPACT after the start of cabozantinib and before the event | Censored | Date of the last tumor assessment prior to the date of initiation of NPACT. |
| No response (no PR and no CR) with at least one radiological or assessment after the initiation of study treatment. | Censored | Date of last radiological assessment |
| No response (no PR and no CR) without any radiological assessment after the initiation of study treatment. | Censored | Date of first cabozantinib intake |

SAP Final: Version 6.0: 17 August 2023

TTR will be calculated as:

TTR (months) = round ((date of initial response or date of last tumour assessment – date of first study drug intake +1) / (30.4375), .01)

In case of incomplete date of first study drug intake, no imputation will be used.

In case of response and a partial initial response date, missing day will be imputed by the last day of the month. This will be the most conservative approach considering the latest date for the response. It will be imputed by the first study drug intake in case the first study drug intake is earlier than the imputed date.

In case of censoring and a partial last tumour assessment date, missing day will be imputed by the first day of the month. It will be imputed by the first study drug intake in case the first intake is later than the imputed date. The censoring may occur earlier than the exact date.

(3) Duration of response (DOR)

DOR is defined as the time from first documented response (PR or CR) to either disease progression or death due to any cause, whichever occurs first. DOR will be analysed for responding subjects only. For responding subjects (i.e. subjects with a PR or CR) who are not known to be dead or progressed at the time of data cut-off for DOR analysis, the DOR will be censored at the last tumour assessment and considering the censoring rules defined in the table below.

| Event | Decision | Date of event or censoring |
|---|--------------|---|
| Progressive disease with no more than one missing scheduled tumor assessment before the event and without NPACT before the event. | Not censored | Date of first progressive disease |
| Death with no more than one missing scheduled tumor assessment before the event and without NPACT before the event. | Not censored | Date of death |
| PD or death with two or more missing scheduled tumor assessments before the event | Censored | Date of the last tumor assessment prior to the missing assessment. |
| PD or death with NPACT after the start of cabozantinib and before the event | Censored | Date of the last tumor assessment prior to the date of initiation of NPACT. |
| No event (no PD, no death) with at least one radiological assessment after the first response to treatment. | Censored | Date of last radiological assessment |

SAP Final: Version 6.0: 17 August 2023

| | | |
|---|----------|-------------------------------------|
| No event (no PD, no death) without any radiological assessment after the first response to treatment. | Censored | Date of first response to treatment |
|---|----------|-------------------------------------|

DOT will be calculated as:

DOT(months) = round ((progression date or death date or date of last tumour assessment – date of initial response+1) / (30.4375),0.01)

In case of non-censoring and a partial progression/death date, missing day will be imputed by the first day of the month. This will be the most conservative approach considering that the earliest date for progression/date. It will be imputed by the date of initial response in case the date of initial response is later than the imputed date.

In case of censoring and a partial last tumour assessment date, missing day will be imputed by the first day of the month. It will be imputed by the date of initial response in case the initial response is later than the imputed date. The censoring may occur earlier than the exact date.

(4) Time-to-Progression for Progression-Free Survival (PFS) analysis

PFS is defined as the time from start of study treatment to either disease progression (as determined by independent central review per RECIST 1.1) or death due to any cause, whichever occurs first. For subjects who are not known to have died or progressed at the time of data cut-off for PFS analysis, the PFS will be censored at the last tumour assessment and considering the censoring rules defined in the table below.

| Event | Decision | Date of event or censoring |
|---|--------------|---|
| Progressive disease with no more than one missing scheduled tumor assessment before the event and without NPACT before the event. | Not censored | Date of first progressive disease |
| Death with no more than one missing scheduled tumor assessment before the event and without NPACT before the event. | Not censored | Date of death |
| PD or death with two or more missing scheduled tumor assessments before the event | Censored | Date of the last tumor assessment prior to the missing assessment. |
| PD or death with NPACT after the start of cabozantinib and before the event | Censored | Date of the last tumor assessment prior to the date of initiation of NPACT. |
| No event (no PD, no death) with at least one radiological | Censored | Date of last radiological assessment |

SAP Final: Version 6.0: 17 August 2023

| | | |
|---|----------|-----------------------------------|
| assessment after the initiation of study treatment. | | |
| No event (no PD, no death) without any radiological assessment after the initiation of study treatment. | Censored | Date of first cabozantinib intake |

PFS will be calculated as:

$$\text{PFS (months)} = \text{round} ((\text{date of progression or date of death or date of last tumour assessment} - \text{date of first study drug intake} + 1) / (30.4375), .01)$$

In case of incomplete date of first study drug intake, no imputation will be used.

In case of non-censoring and a partial progression/death date, missing day will be imputed by the first day of the month. This will be the most conservative approach considering that the earliest date for progression/death. It will be imputed by the first study drug intake in case the first study drug intake is later than the imputed date.

In case of censoring and a partial last tumour assessment date, missing day will be imputed by the first day of the month. It will be imputed by the first study drug intake in case the first intake is later than the imputed date. The censoring may occur earlier than the exact date.

(5) Time-to-death for Overall Survival (OS) analysis

OS is defined as the time from the start of treatment until death due to any cause. For subjects who are not known to be dead at the time of data cut-off for OS analysis, the OS will be censored at the time they were last known to be alive. OS will be calculated as:

$$\text{OS (months)} = \text{round} ((\text{date of last known alive or death date} - \text{date of first study drug intake} + 1) / (30.4375), .01)$$

| Event | Decision | Date of event or censoring |
|---------------------|--------------|----------------------------|
| Death | Not censored | Death date |
| No event (no death) | Censored | Date of last known alive |

In case of incomplete date of first study drug intake, no imputation will be used.

In case of non-censoring and a partial death date, missing day will be imputed by the first day of the month. This will be the most conservative approach considering the earliest date for the death. It will be imputed by the first study drug intake in case the first study drug intake is later than the imputed date.

In case of censoring and a partial last known alive date, missing day will be imputed by the first day of the month. It will be imputed by the first study drug intake in case the first intake is later than the imputed date. The censoring may occur earlier than the exact date.

SAP Final: Version 6.0: 17 August 2023

(6) Fksi-DRS Total Score

Following the Functional Assessment of Cancer Therapy – Kidney Symptom Index – Disease Related Symptoms (Fksi-DRS) Scoring Guidelines Version 4 [4], the 9 item answers will be coded as: “Not at all” = 0, “A little bit” = 1, “Some-what” = 2, “Quite a bit” = 3, and “Very much” = 4.

When at least 50% of items (i.e. 5 items) were answered in the subject questionnaire, the Fksi-DRS Total Score will be calculated as follows.

First, each item will be reversed by doing 4 minus the answer. Then, these individual reversed items will be summed to obtain a score. In last step, this score will be prorated by multiplying by the total number of items in the subscale (i.e. 9) and by dividing by the number of items answered in the questionnaire. This will produce the symptom index score.

The score ranges from a minimum possible score of 0 to a maximum possible score of 36.

As with all FACIT questionnaires, a high score is good. Therefore, a score of “0” is a severely symptomatic subject and the highest possible score is an asymptomatic subject.

(7) Changes from Baseline

Changes from Baseline will be calculated as a difference from Baseline (e.g. assessment at the visit – assessment at Baseline).

(8) Percent change from Baseline

Percent change from Baseline will be calculated as a percentage of change from Baseline (e.g. $100*((\text{assessment at the visit} - \text{assessment at Baseline}) / (\text{assessment at Baseline}))$).

(9) Percent change from nadir

Nadir is the smallest sum of measurements at prior timepoints (including baseline). Percent change from nadir will be calculated as a percentage of change from nadir (e.g. $100*((\text{assessment at the visit} - \text{assessment at nadir}) / (\text{assessment at nadir}))$).

(10) Algorithm for TEAE flag

An AE will be classified as a TEAE in case AE start date is between the first dose of study drug and the last study drug administration plus 30 days.

In case of an incomplete AE start date, an AE start date imputation algorithm will be implemented as described in the Table below. Classification of adverse event according to its treatment-emergent status is then performed using the imputed date.

In the following table, all dates are presented using an YYYY-MM-DD format. As an example, suppose first dose of study drug is equal to 2002-08-11 and several AEs have incomplete start dates.

SAP Final: Version 6.0: 17 August 2023

| Description of incomplete AE start date | Imputed numeric date | Example | |
|---|--|----------------|--|
| | | Character date | Imputed AE start date |
| Day is missing | | | |
| YYYY-MM < YYYY-MM of first dose of study drug | YYYY-MM-01 | 2002-07-XX | 2002-07-01 |
| YYYY-MM = YYYY-MM of first dose of study drug | Min (first dose of study drug, AE end date) or first dose of study drug in case AE end date is missing | 2002-08-XX | Min (2002-08-11, AE end date) or 2022-08-11 in case AE end date is missing |
| YYYY-MM > YYYY-MM of first dose of study drug | YYYY-MM-01 | 2002-09-XX | 2002-09-01 |
| Day and month are missing | | | |
| YYYY < YYYY of first dose of study drug | YYYY-01-01 | 2001-XX-XX | 2001-01-01 |
| YYYY = YYYY of first dose of study drug | Min (first dose of study drug, AE end date) or first dose of study drug in case AE end date is missing | 2002-XX-XX | Min (2002-08-11, AE end date) or 2022-08-11 in case AE end date is missing |
| YYYY > YYYY of first dose of study drug | YYYY-01-01 | 2003-XX-XX | 2003-01-01 |
| Day, month, and year are missing | | | |
| XXXX-XX-XX | Min (first dose of study drug, AE end date) or first dose of study drug in case AE end date is missing | | Min (2002-08-11, AE end date) or 2022-08-11 in case AE end date is missing |

YYYY = non-missing year, MM = non-missing month, DD = non-missing day, XX = missing field.

In case the AE start date is missing, the most conservative approach will be systematically considered and the AE will be considered as a TEAE, except if other data (e.g. end date) indicates differently.

If AE end date is partial, imputation could be done assuming the latest possible date (i.e. last day of month if day unknown, or 31st of December if day and month are unknown).

(11) Time from first study dose for adverse event

If the start date of the adverse event is identical to the date of first administration, then “<1” day will be presented.

The time will be calculated as (AE start date – first administration date)+1 and presented in days.

If the AE start date is partial due to missing day, the time from first dose will be presented as a superior inequality (e.g.: for an AE started in FEB2004 after the first administration performed on 31JAN2004, the time from first dose will be as “≥2” days).

If the first administration date is partial due to missing day, the time from first dose will be presented as a superior inequality (e.g. for an AE started on 01FEB2004 after the first administration performed in JAN2004, the time from first dose will be as “≥2” days).

If both the AE start day and the first administration day are missing, the time from first dose will not be presented.

If the AE start month is missing or the first administration month is missing, the time from first dose will not be presented.

SAP Final: Version 6.0: 17 August 2023

If the AE start date is missing or the first administration date is missing, the time from first dose will not be presented.

(12) Neutrophils values

In some cases, laboratory data may not be reported as they may be difficult to detect. When the White Blood Cells counts (WBC) are recorded, and if $WBC < 0.5*10^9/L$, then neutrophils value will be imputed as zero and thus will be considered to be in NCI grade 4.

(13) NCI-CTC AE grades for laboratory parameters

For NCI/CTC gradable laboratory parameters, appropriate grades should be attributed according to the coding rules specified in the National Cancer Institute for Adverse Events (NCI-CTCAE) version 5.0 if this grade is not present in the database.

(14) Urinalysis

Improved is Positive to Trace or Negative, and Trace to Negative. Worsened is Negative to Trace or Positive, and Trace to Positive, with the result classified as Normal. Abnormal worsening is Negative to Trace or Positive, and Trace to Positive, with the result classified as Abnormal.

(15) BMI

BMI (kg/m^2) will be derived as $Weight (kg)/[Height at Baseline (cm)/100]^2$ and rounded to the nearest decimal.

(16) Algorithm for Prior/ Concomitant flag

Medication, therapies and procedures start and stop dates will be compared to the date of the first dose of study drug to allow classification as either Prior only, Prior and Concomitant, or Concomitant only.

In case of partial start and/or stop medication/ non-drug therapies/surgical procedures dates, imputation will be performed to determine the classification:

- If a partial start date, the first day of the month will be imputed for missing day and January for missing month,
- If a partial stop date, the last day of the month will be imputed for missing days and December will be imputed for missing month.

In case incomplete start or stop date does not allow the classification, the most conservative approach will be systematically considered and the medication will be classified as prior and concomitant.

(17) Time from Diagnosis to Screening

Time from Diagnosis to Screening will be calculated as (date of screening – date of diagnosis). It will be then divided by 30.4375 to be presented in months.

In case of missing screening day, the day will be imputed to 15. In case of missing screening month, the month will not be imputed.

In the same way, in case of missing diagnosis day, the day will be imputed to 15. In case of missing diagnosis month, the day and month will be imputed to 01JUL. No imputation will be performed for missing year.

SAP Final: Version 6.0: 17 August 2023

(18) Treatment duration on 1st anti-cancer therapy

Treatment duration on 1st anti-cancer therapy will be calculated as (latest stop date – earliest start date)+1. It will be then divided by 30.4375 to be presented in months.

In case of missing drug start day, the day will be imputed to 15. In case of missing drug start month, the month will not be imputed.

In the same way, in case of missing drug stop day, the day will be imputed to 15. In case of missing drug stop month, the month will not be imputed.

No imputation will be performed for missing year.

In case, the duration treatment cannot be derived as <6 months, or ≥ 6 months based on the available data, the subgroup ≥ 6 months will be considered by default.

(19) Study exposure

Study exposure will be calculated as:

Study exposure (days) = last visit attended – informed consent date +1. It will be then divided by 30.4375 to be presented in months.

(20) Study drug exposure

a) Total study drug exposure will be calculated as:

Total study drug exposure (days) = last study drug intake date – first study drug intake date +1. It will be then divided by 30.4375 to be presented in months.

b) Actual study drug exposure will exclude the study drug interruptions.

For interim analysis, the last attended visit date will be considered as the last study drug intake date, in case the subject has not ended the treatment prior to this visit.

(21) Average daily dose

Average daily dose in mg/day will be calculated as the number of tablets taken multiplied by the corresponding dosage in mg from each kit, and divided by the total study drug exposure in days (i.e. including the study drug interruptions).

(22) Age

Subject age (years) will be derived as (screening year – birth year).

(23) Compliance

The compliance will be calculated as :

Total number of tablets taken divided by Total number of tablets planned to be taken multiplied by 100.

Total number of tablets planned to be taken will be calculated as (last study drug intake date – first study drug intake date)+1, as the planned intake is one tablet per day.

(24) Study day

Study day will be defined as ‘-1’ for the day prior to treatment and as ‘1’ for the day of the first intake of study treatment (i.e. day 0 does not exist).

SAP Final: Version 6.0: 17 August 2023

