## **RESPONSE CRITERIA**

### **CRITERIA FOR TARGET LESIONS**

Definitions of the criteria used to determine objective tumour response for target lesions are provided below:

- Complete response (CR): Disappearance of all target lesions
  - Any pathological lymph nodes must have reduction in short axis to < 10 mm.
- Partial response (PR): At least a 30% decrease in the sum of diameters of all target lesions, taking as reference the baseline sum of diameters, in the absence of CR
- Progressive disease (PD): At least a 20% increase in the sum of diameters of target lesions, taking as reference the smallest sum of diameters at prior timepoints (including baseline)
  - In addition to the relative increase of 20%, the sum of diameters must also demonstrate an absolute increase of  $\geq 5$  mm.
- Stable disease (SD): Neither sufficient shrinkage to qualify for CR or PR nor sufficient increase to qualify for PD

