| 12-lead ECG | ≤15 Days prior to baseline | X (prior to first dose) ^f | | X | | Every 12 weeks | X | |
| Haematology and blood biochemistry | ≤15 Days prior to baseline | X (prior to first dose) ^f | X | X | X | Every 4 weeks | X | |
| Coagulation assessments | ≤15 Days prior to baseline | X (prior to first dose) ^f | X | X | X | Every 4 weeks | | |
| Urinalysis, microscopic urine examination and urine chemistry (including UPCR) ^g | ≤15 Days prior to baseline | X (prior to first dose) ^f | X | X | X | Every 4 weeks | X | |
| Pregnancy test (female subjects only, if applicable) | ≤7 days prior to baseline | X (prior to first dose) ^f | Urinary and/or pregnancy blood tests are mandatory at every visit | | | | X | |
| Thyroid function test (FT4, TSH) | ≤15 days prior to baseline | X (prior to first dose) ^f | Every 4 weeks | | | | X | |
| Chest/Abdomen/Pelvis (C/A/P) CT/MRI | ≤28 days prior to baseline | X ^f | Every 12 weeks (±10 days) while on protocol treatment beginning at Week 12 (i.e. Week 12, Week 24, Week 36, etc) until the end of study and additionally if clinically indicated | | | | | X ^h |
| Brain CT/MRI and Bone scintigraphy Scan (only if indicative of metastases) | ≤28 days prior to baseline | Only if indicative of brain and/or bone metastases at screening or if signs or symptoms suggestive of metastases develop | | | | | | X ^h (only if indicative of metastases) |

CONFIDENTIAL

SAP Final: Version 6.0: 17 August 2023

| | Pre-treatment Period | Treatment Period | | | | | | Post-treatment Follow-up Period ^d |
|--|-----------------------------------|---|---|------------------------|------------------------|---------------------------------|--|--|
| Assessment | Screening | Baseline ^a | Week 2 | Week 4 | Week 8 | Every 4 weeks | End of Study Treatment Visit ^b or Early Study Withdrawal Visit ^c | Follow-Up |
| | Visit 1 | Visit 2 | Visit 3 | Visit 4 | Visit 5 | Visit 6 to Visit X | 30 days after the last dose of treatment | Every 12 weeks |
| | Before first cabozantinib intake | Day 1 | Day 15 (± 2 Days) | Day 29 (± 2 Days) | Day 57 (± 2 Days) | Day 85 to Day X (± 5 Days) | (+15 Days) | (± 15 Days) |
| Cabozantinib intake ⁱ | | All subjects will be treated with oral cabozantinib 60 mg once daily (q.d.). In case of treatment-emergent toxicity, the Investigator may decide to reduce the dose to 40 mg or 20 mg | | | | | | |
| Dispense/return of oral study drug and compliance accounting | | X | | X | X | X | X | |

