The secondary efficacy endpoints are:

- (a) TTR defined as the time from start of study treatment to the date of first evidence of response (PR or CR as determined by independent central review per RECIST 1.1) (see [Appendix 1 \(2\)](#), for the derivation and censoring rules).
- (b) DOR defined as the time from first documented response (PR or CR as determined by independent central review per RECIST 1.1) to either disease progression (as determined by independent central review per RECIST 1.1) or death due to any cause. Censoring rules will be similar to those applied for progression-free survival (PFS) (see [Appendix 1 \(3\)](#)).

SAP Final: Version 6.0: 17 August 2023

- (c) DCR defined as the proportion of subjects with a BOR of a PR, CR or SD as determined by independent central review per RECIST 1.1
- (d) PFS defined as the time from start of study treatment to either disease progression (as determined by independent central review per RECIST 1.1) or death due to any cause, whichever occurs first (see [Appendix 1 \(4\)](#)).
- (e) ORR in cohort B defined as the proportion of subjects with a BOR of a PR or CR at any timepoint as determined by independent central review per RECIST 1.1
- (f) OS defined as the time from the start of treatment until death due to any cause (see [Appendix 1 \(5\)](#)).
- (g) ORR, TTR, DOR, DCR and PFS according to local Investigator's review per RECIST 1.1 and defined as for the independent central review,
- (h) Change in disease-related symptoms as assessed by the FKSI-DRS questionnaire.

The endpoints of ORR, TTR, DOR, DCR and PFS will be evaluated by tumour assessments (see [Section 1.3.2.1](#)). The OS will be assessed as described in [Section 1.3.2.1](#).

All these secondary endpoints will be presented in each cohort separately. In addition, ORR and PFS according to local Investigator's review per RECIST 1.1 as well as OS will be presented in the overall population (cohort A + cohort B).

Below is the **definition of the estimand** used for the secondary efficacy endpoint of duration of response:

Treatment : Cabozantinib

Population : Subjects with unresectable, locally, advanced or metastatic RCC with a clear-cell component who progressed after prior CPI therapy with ipilimumab and nivolumab in combination (Cohort A) with a PR or CR at any timepoint during the treatment period.

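### SAP Appendix 1 (1) codes documented progression after a missed Week 12 scan as not evaluable, which mislabels best overall response for those patients

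*SAP*

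**What the plan says.** SAP Section 3.1.1 defines ORR through BOR and sends the derivation to Appendix 1 (1). That item treats a scan missed at visit n according to what visit n+1 shows. If n+1 is PD, the missing scan is left alone: "it should be kept missing as long as the next evaluation at visit n+1 is a Progressive Disease (PD"). Two outcomes follow. The first is "The best overall response (BOR) in this case is 'not evaluable' if there are no previous assessments". The second is "Otherwise, the best overall response will be assessed by using tumour assessments up to visit n-1".

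Scans are scheduled every 12 weeks from Week 12 (SAP Section 1.3.2.1 and Table 2), so no scheduled post-baseline scan comes before Week 12. For PFS, the first row of the table in SAP Appendix 1 (4) treats this situation as an event, not censored: "Progressive disease with no more than one missing scheduled tumor assessment before the event and without NPACT before the event". Protocol Appendix 5 makes a patient with no imaging not evaluable at that timepoint only, and its Table A5.1 gives overall PD whenever target lesions show PD.

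SAP Section 3.1.2 has "DCR defined as the proportion of subjects with a BOR of a PR, CR or SD". SAP Section 3.2.13 bases percentages outside the disposition tables on non-missing data and does not say whether NE counts as missing.

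**The concern.** A patient whose first evaluable scan after baseline shows progression has a known outcome. The BOR rule discards it because an earlier scan was not done. The same patient is then a dated progressor in the PFS table and not evaluable in the BOR table, and the SAP departs from the protocol's own response criteria.

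At stake is the split between PD and NE in the BOR results by IRC and by investigator, and the labels in concordance Table 14.2.4.3. A reader who uses the PD share to judge how many patients were refractory would see too few. A second question is whether the NE label could remove the patient from a denominator.

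**Working it through.** **Step 1. One patient under each rule.** Assume a baseline target lesion, no Week 12 scan, no unscheduled scan, no other anti-cancer therapy, and PD at Week 24.

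| Rule | Result |
|---|---|
| SAP Appendix 1 (1): n = Week 12 missing, n+1 = Week 24 PD, nothing earlier | BOR = NE |
| Protocol Appendix 5, missing assessments | NE at Week 12 only |
| Protocol Appendix 5, Table A5.1 | Overall response PD at Week 24 |
| SAP Appendix 1 (4): PD after one missed scan | Uncensored PFS event on the PD date |

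This reads the earlier assessments in the SAP rule as post-baseline ones. If baseline counted, BOR would rest on baseline alone, which yields no response category, so the PD is lost either way. The other branch does no harm where the earlier result is CR, PR or SD, because that result is better than the later PD and is the best response in any case.

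**Step 2. The plan's own figures.** Inputs (Protocol synopsis, sample size): null 10%, alternative 23%, one-sided 0.025, exact binomial, 68 evaluable, 7% non-evaluable.

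- At n = 68, the smallest r with P(X ≥ r | 0.10) ≤ 0.025 is 13, with exact alpha 0.0163. Power is P(X ≥ 13 | 0.23) = 81.6%, against 80% stated.
- 68 / (1 − 0.07) = 73.1, rounded up to 74, as stated. At n = 74, r = 14, alpha is 0.0142 and power is 83.4%.

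These figures reproduce, and none depends on whether a non-responder is labelled PD or NE.

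**Step 3. Size of the mislabelling.** With k such patients, the PD share is too low and the NE share too high by k/N.

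- N = 68: 1/68 = 1.47 points per patient.
- N = 74: 1/74 = 1.35 points per patient. SAP Section 5 says cohort A exceeds 74, so the figure would be slightly smaller still if more than 74 are evaluable.
- The documents give no k. For an assumed 1 to 5 patients at N = 68, the range is 1.5 to 7.4 points (5/68 = 7.35%).

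**Step 4. Effect on DCR and ORR.** PD and NE are both outside the two numerators. With NE kept in the denominator, moving a patient between them changes each rate by 0.

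If NE were treated as missing and dropped, both rates would rise. In an assumed example with N = 68, 51 patients with disease control and 16 responders:

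| NE dropped | DCR | ORR |
|---|---|---|
| 0 | 51/68 = 75.0% | 16/68 = 23.5% |
| 1 | 51/67 = 76.1% | 16/67 = 23.9% |
| 5 | 51/63 = 81.0% | 16/63 = 25.4% |

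For the primary test, 13 responders are still required at n = 67 and at n = 66, so dropping one or two patients would not move the threshold.

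**The case against.** The strongest reply is that little depends on this. BOR is not a listed endpoint in the current protocol. No secondary endpoint is tested against a threshold, the progression is captured in PFS, and responses are listed by subject. The case is also narrow: the patient must miss Week 12, have no unscheduled scan, remain in the study and then be scanned at Week 24. All of this stands and keeps the point minor. It does not make the BOR category right.

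The effect on concordance is also limited. A scan that was not done is missing for both readers. If both then call PD, the pair moves from PD/PD to NE/NE and stays on the diagonal of Table 14.2.4.3. The labels are wrong, but that agreement is kept.

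On the denominator, the primary estimand in SAP Section 3.1.1 makes patients without any post-baseline scan, or withdrawn without response, non-responders. That suggests NE is meant to count as failure for ORR. It does not literally cover a patient who has a post-baseline scan showing PD, and it says nothing about DCR.

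A reader might infer something stronger: that DCR is overstated because SD on an early unscheduled scan counts as disease control. It is true that SD in Protocol Appendix 5 is a size criterion only ("Neither sufficient shrinkage to qualify for CR or PR nor sufficient increase to qualify for PD"), that no minimum interval is given, and that scans run "until the end of study and additionally if clinically indicated". But no text says that an early SD enters BOR. The rule works by visit, the tumour windows in SAP Section 3.2.12 leave Days 1 to 70 unallocated, and the IRC charter, to which further detail is referred, is not among the documents. That is under-specification. The documents set no interval against which DCR could be called wrong.

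**Conclusion.** The rule is wrong as written for a narrow group. Documented PD after a missed Week 12 scan, with no earlier post-baseline assessment, becomes a BOR of NE, against Protocol Appendix 5 and against the SAP's own PFS rule. The PD/NE split is off by 1.47 points per patient at N = 68. The number of such patients is unknown, and any total is an assumption.

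ORR, DCR and the primary test are not affected on the condition that NE patients stay in the denominator as failures. SAP Section 3.2.13 does not settle that, so it should be stated. It would be an overreach to conclude from this rule that DCR is biased, or to put a figure on a DCR overstatement from early SD. Severity: minor.

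**What to change.** In SAP Appendix 1 (1), replace the sentence that assigns NE with: *if there is no earlier post-baseline assessment and PD is documented after no more than one missed scheduled assessment, BOR is PD*. Apply it to IRC and investigator BOR alike. The limit of one missed scan matters. Without it, a patient who missed Weeks 12 and 24 and had PD at Week 36 would be PD in BOR but censored in PFS, which is a new mismatch.

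Add one sentence, in Section 3.2.13 or beside the ORR and DCR definitions, that NE patients remain in both denominators as failures.

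Separately, ask the sponsor to state the minimum interval for SD, if one is intended, and how scans on Days 1 to 70 enter BOR. This is a request for clarification.

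The cost is two SAP sentences and a small program change. The sample size and the test do not change.
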